  - Percentage of subjects having at least "Improved" according to the GAIS on both sides of the face combined, as assessed live by the subject and the Treating Investigator separately, at all visits following the Baseline visit for the Treatment Group and at month 7, 9 and 12 for the Control Group: percentage will be displayed along with 95% confidence intervals for each treatment group via Clopper-Pearson method.
  - Percentage of subjects responding in each response category for each question in the subject satisfaction questionnaire at all visits following the Baseline visit for the Treatment Group: percentage will be displayed for each category.
  - Change from baseline in subject satisfaction using the Satisfaction with Cheeks FACE-Q questionnaire with Outcome Rasch transformed total scores at all visits following the Baseline visit for the Treatment Group and at month 7, 9 and 12 for the Control Group: for each treatment group, summary statistics and 95% confidence interval calculated for each treatment mean via t-distribution will be displayed.
  - Proportion of subjects in each response category for each of the individual questions using the Satisfaction with Cheeks FACE-Q questionnaire with Outcome Rasch transformed total scores as well as at all visits following the Baseline visit for the Treatment Group and at month 7, 9 and 12 for the Control Group: percentages will be displayed for each category.
  - Time to feeling comfortable returning to social engagement after treatment (defined as the subject diary date with the first "yes" for "Did you feel comfortable returning to social engagement today?" minus the date of the corresponding treatment) will be analyzed using Kaplan-Meier methods. The median time to feeling comfortable will be estimated and Kaplan-Meier plots will be created.

Doc id

Time to feeling comfortable returning to social engagements will be calculated for each diary (treatment occasion) separately: after 1st treatment, 2nd treatment, etc. Subjects who never report feeling comfortable during each time period will have their response time censored at the time of their last diary entry in each period.

2.4.6 Other effectiveness endpoints:

Some subjects' dermal thickness ultrasounds were taken using an incorrect gain (an ultrasound setting which brightens the image by a uniform margin). To ensure this does not compromise efficacy results, two summaries of dermal thickness will be provided – the first will be a summary using all subjects, regardless of their gain setting. The second summary will be a sensitivity analysis, which will compare two groups at each visit: subjects with correct gain vs. subjects with incorrect gain (correct gain defined as subjects who had the same gain at the baseline visit and the visit being analyzed; conversely, incorrect gain defined as subjects who had a different gain at the baseline visit compared to the visit being analyzed). Gain information at each subject-visit will be included in a listing.

## 2.5 Safety Analysis

Safety endpoints will be summarized using descriptive statistics by treatment group based on the safety population using the Observed Cases (OC). There are no planned inferential statistical analyses of safety endpoints.

## 2.5.1 Treatment Administration, Procedural Anesthetics, and Injection Concomitant Procedures

Treatment administration endpoints that will be summarized by treatment session include (but are not limited to):

- Injection volume
- Injection method
- Depth of injection.

The number of subjects with any procedural anesthetics will be summarized by type and location.

The number of subjects with any injection concomitant procedures will be summarized.

## 2.5.2 Pre-Defined Expected Post-Treatment Symptoms

Number and percentage of subjects reporting each pre-defined, expected, post-treatment symptoms, as collected in the 28-day diary, will be presented by treatment group in total and by maximum intensity. Number of days with the event will be presented by treatment group and category: 1, 2-7, 8-14, and 15-28 days

### 2.5.4 Other Safety Analyses

Functionality, vision function assessments, sensation, firmness, symmetry, mass formation and palpation assessments, and device deficiencies will be analyzed descriptively as appropriate.

Snellen visual acuity will be summarized using Snellen decimal categories. Snellen ratios will be converted to decimals (e.g., 20/25=0.8, 20/30=0.67, 20/70=0.29) and categorized with Snellen decimal categories of >=0.8, 0.32 to <0.8, 0.125 to <0.32, 0.05 to <0.125, and <0.05. Each subject's eye will be categorized by the number of Snellen decimal categories worsened (0 if improved or no change), and the frequency of these changes will be summarized across subject-eyes.

For example, if (a,b) represent individual change in each subject's eyes, then possible values for a and b are 0+, -1, and -2, where 0+ = improvement or no change in Snellen decimal category, -1= worsening by 1 Snellen decimal category, -2 = worsening by 2 or more Snellen decimal categories. NA = Not available. Then, (-2, -2) represents a worsening of at least 2 Snellen decimal categories in both eyes, and (0+,-1) represents an improvement or no change in one eye and a worsening by 1 Snellen decimal category.

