- 9. Treatment with chemotherapy, immunosuppressive agents (inhaled corticosteroids allowed), immunomodulatory therapy (e.g. monoclonal antibodies or antiviral treatment for HIV or Hepatitis C) within 6 months before treatment.
- 10. Use of topical corticosteroids or topical prescription retinoids (in the treatment area) within 1 month of the Baseline visit or systemic retinoid treatment within 6 months of the Baseline visit.
- 11. Previous surgery including plastic surgery, lifting threads, tissue grafting or tissue augmentation with permanent implants, silicone or fat, or tattoo, affecting the treatment area.
- 12. History of cancer or previous radiation near or on the area to be treated.
- 13. HIV positive or active hepatitis.
- 14. History of or active collagen diseases such as systemic lupus erythematosus, rheumatic arthritis, polymyositis, dermatomyositis, skin or systemic scleroderma.
- 15. Tendency to form keloids, hypertrophic scars, or any other healing disorder.
- 16. Presence of piercing, beard or facial hair that could interfere with study evaluation.
- 17. Abnormal result on functionality, sensation, symmetry, mass formation or palpation assessments in the treatment area.
- 18. Abnormal result on extraocular muscle function test or confrontational visual field assessment.
- 19. Presence of a dental, oral, or facial condition which, in the Treating Investigator's opinion, would interfere with the study injections and/or study assessment, e.g. has dentures or any device covering all or part of the upper palate, and/or severe malocclusion or dentofacial or maxillofacial deformities.
- 20. Woman who is pregnant (confirmed by positive urine pregnancy test/serum pregnancy test), breast-feeding or intend to become pregnant over the duration of the study.
- 21. Any medical condition that, in the opinion of the Treating Investigator, would make the subject unsuitable for inclusion (e.g. a chronic, relapsing or hereditary disease that may interfere with the outcome of the study).
- 22. Other condition preventing the subject from entering the study in the Treating Investigator's opinion, e.g. subjects failing baseline safety assessments, subjects not likely to avoid other

5.0

cosmetic treatments in the treatment area, subjects anticipated to be unavailable or incapable of understanding the study assessments or having unrealistic expectations of the treatment result.

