8.4 Visual Function assessments

Visual function assessments will be performed for all subjects. For subjects in the treatment group, the assessments will be performed both prior to and post injection of the study product at baseline and all scheduled treatment visits. The post-treatment assessments should be performed 30 min after the injections are completed. In the event of blindness or any significant ophthalmic sign or symptom,

subjects are to undergo immediate evaluation by an ophthalmologist or a retina specialist. All incidences of visual disturbances, regardless of relationship to study product or seriousness, are considered Adverse Events of Special Interest (AESIs) and include but are not limited to the following: any loss of vision, blurry vision, double vision, pain in or around the eye, blind spot or shadow in the visual field, trouble moving eyes. AESI's should be reported (using the Adverse Event Clarification Form) within 24 hours of awareness. Please refer to recording instructions in section 8.6.6.

8.4.1 Snellen visual acuity test

A Snellen Eye Chart will be used to assess visual acuity for distance vision. Visual Acuity will be conducted using the subject's best distance correction (e.g. with contacts or spectacles) at a distance of 6 feet from the chart. Each eye will be measured separately by either using an occluder or having the subject cover one eye at a time. The subject will be asked to start reading the letters at the top of the chart working their way to the bottom. The smallest row of letters that the subject can read will indicate their visual acuity listed on the chart. Snellen Visual Acuity will be recorded in their source documentation and eCRF. If there are two or more visual acuity line changes during the course of study, these should be reviewed and assessed by the Investigator for a potential adverse event.

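### The SAP's acuity table counts broad decimal categories, so some losses of two or more chart lines are tabulated as 0+ and the protocol's two-line review trigger cannot be read from it

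*SAP*

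**What the plan says.** Protocol 8.4.1 records acuity for each eye by chart row: "The smallest row of letters that the subject can read will indicate their visual acuity listed on the chart". Its trigger for follow-up uses the same unit: "If there are two or more visual acuity line changes during the course of study, these should be reviewed and assessed by the Investigator" as a potential adverse event.

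SAP 2.5.4 uses a different unit. Each ratio becomes a decimal, and the decimals are grouped into "Snellen decimal categories of >=0.8, 0.32 to <0.8, 0.125 to <0.32, 0.05 to <0.125, and <0.05". Each eye is then "categorized by the number of Snellen decimal categories worsened (0 if improved or no change"). In the SAP's example of the tabulated values, "0+ = improvement or no change in Snellen decimal category", -1 is one category worse and -2 is two or more categories worse. The section plans no summary by lines changed. It also does not say which acuity tests are tabulated, although protocol 8.4 requires a test 30 minutes after each injection session as well as one before it.

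**The concern.** Each bounded band covers several chart rows. An eye can therefore lose two lines, enough to trigger Investigator review, and still be tabulated with eyes that improved or stayed the same. An eye that crosses a cut point by a single line is tabulated as worse. The table cannot show how many eyes met the trigger.

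This matters because protocol 2.4 names vision impairment and blindness among the rare but serious risks of intravascular filler injection, protocol 8.6.6 makes every visual disturbance an adverse event of special interest, and visual function is a listed safety endpoint in both documents. SAP 1.2 also makes an acceptable safety profile a condition of study success.

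The affected starting values can occur. The visual exclusion in protocol 5.3 reads "Abnormal result on extraocular muscle function test or confrontational visual field assessment" and sets no limit on acuity.

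**Working it through.** **Inputs.** The conversion, bands and scoring rule come from SAP 2.5.4, and the two-line trigger from protocol 8.4.1. The chart rows are an assumption, because the protocol says only that a Snellen chart is used. Several row sets were therefore tried.

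**1. Reproduce the SAP's conversions.** Decimal = 20 / denominator. 20/25 = 0.80, 20/30 = 0.667, which rounds to 0.67, and 20/70 = 0.286, which rounds to 0.29. All three agree with the SAP: "Snellen ratios will be converted to decimals (e.g., 20/25=0.8, 20/30=0.67, 20/70=0.29").

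**2. Put common rows in their bands.**

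- At least 0.8: 20/10 (2.00), 20/13 (1.54), 20/15 (1.33), 20/20 (1.00), 20/25 (0.80)
- 0.32 to below 0.8: 20/30 (0.67), 20/40 (0.50), 20/50 (0.40), 20/60 (0.33)
- 0.125 to below 0.32: 20/70 (0.29), 20/80 (0.25), 20/100 (0.20)
- 0.05 to below 0.125: 20/200 (0.10)

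**3. Score individual losses.**

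| Loss | Lines, if the chart has the rows between | SAP score |
|---|---|---|
| 20/30 to 20/50 | 2 | 0+ |
| 20/15 to 20/25 | 2 | 0+ |
| 20/30 to 20/60 | 3 (needs a 20/60 row) | 0+ |
| 20/25 to 20/30 | 1 | -1 |
| 20/20 to 20/30 | 2 | -1 |
| 20/25 to 20/40 | 2 | -1 |
| 20/20 to 20/50 | 4 | -1 |

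**4. Count over all possible starting rows.** A chart with r rows has r - 2 possible two-line losses and r - 3 possible three-line losses. The entries are the numbers scored 0+.

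| Assumed chart | Two-line | Three-line |
|---|---|---|
| (a) 8 rows: 20/200, 100, 70, 50, 40, 30, 25, 20 | 1 of 6 (17%) | 0 of 5 (0%) |
| (b) (a) plus 20/15 | 2 of 7 (29%) | 0 of 6 (0%) |
| (c) (a) plus 20/15, 20/10 | 3 of 8 (38%) | 1 of 7 (14%) |
| (d) (a) plus 20/15, 20/13, 20/10 | 4 of 9 (44%) | 2 of 8 (25%) |
| (e) (c) plus 20/60, 20/80 | 5 of 10 (50%) | 2 of 9 (22%) |
| (f) 0.1-logMAR steps, 20/10 to 20/400 | 9 of 15 (60%) | 5 of 14 (36%) |

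On every chart at least one two-line loss scores 0+. On (a) to (e) these always include 20/30 to 20/50. On (f) the nearest equivalent is 20/32 to 20/50.

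**5. Check without a chart.** Band width on the log scale is log10(upper cut / lower cut): log10(0.8/0.32) = 0.398, log10(0.32/0.125) = 0.408, log10(0.125/0.05) = 0.398. Each bounded band is thus about four 0.1-log lines wide. If starting values are spread evenly across a band of width 0.4, a loss of 0.2 stays inside it for (0.4 - 0.2)/0.4 = 50% of starting points, and a loss of 0.3 for (0.4 - 0.3)/0.4 = 25%. Both figures lie within the ranges in step 4.

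**The case against.** **The protocol's two-line rule is not an analysis criterion.** It prompts review at the site and states neither a direction nor a reference visit. A reader might infer that the SAP contradicts a protocol-defined endpoint. It does not: the endpoint is visual function assessments, to be analysed descriptively, and a categorical display is allowed. The SAP also says that 0+ refers to change in category, so the coarse unit is disclosed. This objection stands, and it limits how the added table may be described.

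**The size depends on the chart.** A reader might infer that many two-line losses are hidden, or that the percentages apply to subjects. The documents support neither. On the basic 8-row chart only one two-line loss in six scores 0+, and no three-line loss does. On chart (d), three of the four two-line losses scored 0+ start better than 20/20: 20/10 to 20/15, 20/13 to 20/20 and 20/15 to 20/25. Two-line losses from 20/20 or 20/25 score -1 on charts (a) to (e). It is also no defect that no two-line loss scores -2, because -2 means two categories. This objection stands in full.

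**Other outputs carry the information.** Visual disturbances are reportable within 24 hours whatever their cause, AEs are tabulated by treatment, all eCRF data are listed, and SAP 2.1.2 lets supportive analyses be added without an amendment. This stands in part. AE tables hold only changes that were reported or judged to be events, and under protocol section 8 the unblinded Treating Investigator determines their severity and relatedness. SAP 2.5.3 plans no separate table of visual disturbances. Listings show raw values without a count or a comparison by arm.

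**Conclusion.** The point holds as a mismatch of units in one planned safety table. Some two-line losses, such as 20/30 to 20/50, are tabulated as 0+, and so are some three-line losses if the chart has the rows for them. A one-line step across the 0.8 cut point is tabulated as -1, as is the four-line loss from 20/20 to 20/50. The number of eyes with a change of two or more lines cannot be recovered from the table.

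The mismatch follows directly from the SAP cut points and ordinary Snellen rows. Its size is much less certain: 17% to 60% of possible two-line losses and 0% to 36% of possible three-line losses on the charts assumed, with every possible starting row weighted equally. The documents give no distribution of baseline acuity, so these shares cannot be turned into an expected number of subjects or a measure of how far any signal would be understated. Nor do the documents support saying that vision loss would go unreported, since the AE route and the listings remain.

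**What to change.** Keep the decimal categories in SAP 2.5.4 and add:

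- a table of the number and percentage of eyes, and of subjects, with a loss of two or more lines from baseline, by arm and visit, including the 30-minute post-injection test for treated subjects;
- a listing of those eyes;
- a statement of the chart rows used to count lines.

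The SAP should describe the table as aligned with the review trigger in protocol 8.4.1, not as a protocol-defined endpoint. The direction (loss) and the reference (baseline) are choices made for the table, and the protocol sentence states neither.

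The cost is one table and one listing from acuity values already recorded. No assessment, visit or clinical procedure changes.

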## 2.6 Interim Analysis

There are no planned interim analyses for this study.

Statistical Analysis Plan Version 5.0, 30 Jul 2021

**MA-42004** 

Doc id

#### 2.8 Changes in the Analysis Planned in the Protocol

There have been no substantial changes from the statistical methods described in the protocol.

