10.6 Handling of missing data

Number of missing values will be summarized and reported as appropriate.

For ITT analysis of the Blinded Evaluator At Rest responder rate at month 12 (primary endpoint), missing values will be assumed to be missing due to lack of effect. Therefore the primary method of imputation will use the baseline observation carried forward (BOCF) method. Impact of

. .

missing data on the primary endpoint will be evaluated by performing sensitivity analysis based on the observed cases in the ITT set.

All other effectiveness endpoints will be evaluated based on the observed cases in ITT.

Descriptive statistics of all safety data will be performed on observed cases.

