### **Revision History**

Version

2.0

3.0

4.0

5.0

Galderma Research and Development, LLC	
Confidential and Proprietary	

		2. Many endpoints at month 9 visits are now at month 12 – including primary endpoint
		3. PP population is now based on month 12 visit and primary endpoint
		4. Changed BOCF to Multiple Imputation
		5. Updated schedule of events
		6. Device deficiencies will be summarized
15 JAN 2021	PPD	Added information on multiple imputation for the primary analysis (section 2.4.3 Multiple Imputation )
23 MAR 2021	PPD	1. Amended the number of FST V-VI subjects to be at least 14 in alignment with the protocol amendment v5
		2. Remove an erroneous mention to an unused endpoint, the WAS
		3. Define how nodules, papules, and granuloma are defined from AEs
		
 
Clarify that AE's by injection technique include combinations of injection techniques
 

30 JUL 2021	PPD	1. Moved "other effectiveness endpoints" to new section 2.4.6. Added information here on summarizing subjects with incorrect gain for dermal thickness.
		2. Elaborated on how Snellen acuity will be summarized via Snellen decimal categories.

1.

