### 2.4.2 Handling of Missing Data

Number of missing values will be summarized and reported as appropriate.

For ITT analysis of the Blinded Evaluator responder rate at month 12 (primary endpoint), missing values will be imputed via multiple imputation. Only patients with a baseline

Doc id

score will be included in this analysis. Impact of missing data on the primary endpoint will be evaluated by performing sensitivity analysis based on the observed cases in the ITT set.

A small number of patients may have a month 6 visit rather than month 7. These patients' month 6 visit will be used as a conservative surrogate for their month 7 visit results, and pooled with the month 7 visit data.

All other effectiveness endpoints will be evaluated based on the observed cases in ITT.

Descriptive statistics of all safety data will be performed on observed cases.

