## 2.4.3 Multiple Imputation

The multiple imputation (primary analysis only) will assume Missing Completely at Random (MCAR). Regardless of the actual pattern of missing data, the Full Conditionals (FCS) option of the MI procedure from the SAS® system will be used to generate ten sets of data with missing values imputed from observed data. The observed data used to impute missing Month 12 values for each side of the face are as follows: treatment, side of face, and all previous scores (including the following visits: screening, baseline, and months 7, 9, and 12). The FCS option with no arguments will be employed to model the missing left and right scores separately, which is equivalent to a regression model which uses all variables as covariates. To achieve such a model.

The imputed datasets will be analyzed using the methodology described for the primary analysis. In terms of the continuous mapping of the **multiple** imputation, a responder will be defined as a subject with at least an improvement of 1 in both cheeks concurrently from baseline. Responder rates, difference in responder rates, and the associated confidence intervals will be combined by the MIANALYZE procedure of the SAS® system. The mean value of the Fisher's Exact Test p-values across imputations will be reported. The seed number to be used will be the last four digits of the protocol number (1812).

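### SAP 2.8 reports no substantial change, yet the SAP replaces the protocol's BOCF with multiple imputation for the primary endpoint, and no pre-specified analysis tests the protocol's lack-of-effect assumption

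*SAP*

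**What the plan says.** For the primary endpoint, Protocol 10.6 states that "missing values will be assumed to be missing due to lack of effect", and concludes: "Therefore the primary method of imputation will use the baseline observation carried forward (BOCF) method". Its sensitivity analysis is observed cases in the ITT set.

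For the same endpoint, SAP 2.4.2 states that "missing values will be imputed via multiple imputation". SAP 2.4.3 labels the assumption missing completely at random (MCAR), but imputes each side of the face from treatment and the scores at the other visits, including months 7 and 9. The impact of missing data is to be examined by "performing sensitivity analysis based on the observed cases in the ITT set".

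The SAP revision history has the entry "Changed BOCF to Multiple Imputation", listed among changes taken from CIP V4. SAP 2.1 gives the SAP precedence over the protocol's statistical sections. SAP 2.8, the section for declaring departures from the protocol, says: "There have been no substantial changes from the statistical methods described in the protocol". SAP 1.1 still identifies the protocol as v3.0; the protocol in hand is version 5.0 and specifies BOCF.

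**The concern.** Under BOCF a subject without a month-12 score has zero change, and so cannot meet the responder definition of at least one grade of improvement on both cheeks. Under MI the same subject receives a probability of response predicted from arm and other scores. For the only confirmatory endpoint that is a substantial change, so the sentence in SAP 2.8 is incorrect. The precedence clause settles which method is primary; it does not make 2.8 true, and it takes BOCF out of the plan altogether.

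The larger issue is what remains. The protocol gives a reason why data would be missing, namely that treatment did not work. MI given observed scores and observed cases both assume that missingness does not depend on the unobserved outcome, so neither can show what happens if the protocol's reason is right. Only the evaluator is blinded (Protocol 4.4.2) and the control is no treatment, so subjects know their arm, and dropout related to outcome or arm is possible.

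**Working it through.** **Inputs.** Responder rates of 70% and 35%, evaluable samples of 84 and 42, about 90% power, 15% dropout, 2:1 allocation, about 150 randomized (Protocol 10.9.2 and 10.9.3, SAP 2.7). Two-sided Fisher's exact test, p < 0.05 (SAP 2.4.4). The documents give no dropout by arm; every split below is an assumption.

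**1. The plan's own figures.** (84 + 42)/0.85 = 148.2, rounded up to 149, which agrees with about 150. Power at 84/42 for 70% vs 35% is 95.7% by exact Fisher enumeration and 97.0% by the pooled normal formula, so the stated 90% is not reproduced. It errs on the safe side and is separate from this point.

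**2. Effect of counting missing as non-response.** With completer rate p and missing fraction m, the rate on the full ITT arm is p × (1 − m). Taking the planning rates as the completer rates and m = 15% in both arms:
- Treated: 0.70 × 0.85 = 59.5%.
- Control: 0.35 × 0.85 = 29.75%.
- Difference: 29.75 points instead of 35.

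**3. Power.** Power is the summed binomial probability of all tables with Fisher p < 0.05. Non-responder analysis at 100/50: 92.4%. The like-for-like comparator is observed cases with the same 15% missing. Since 50 × 0.85 = 42.5, this is 95.4% at 85/42 and 96.6% at 85/43.

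**4. Unequal dropout (assumed).**

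| Missing, treated/control | Missing of 150 | Non-responder rates | Difference | Power, non-responder (100/50) | Power, observed cases |
|---|---|---|---|---|---|
| 15%/15% | 15% | 59.5% vs 29.75% | 29.75 | 92.4% | 95.4% |
| 20%/5% | (20 + 2.5)/150 = 15% | 56.0% vs 33.25% | 22.75 | 72.1% | 97.1% |
| 10%/20% | (10 + 10)/150 = 13.3% | 63.0% vs 28.0% | 35.0 | 98.1% | 95.6% |
| 5%/30% | (5 + 15)/150 = 13.3% | 66.5% vs 24.5% | 42.0 | 99.9% | 94.7% |

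If missingness is unrelated to outcome, MI and observed cases target 35 points in every row. Power under MI was not calculated, because it depends on correlations between visits that the documents do not give.

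**5. The reverse direction.** With a true rate of 35% in both arms and 5%/30% missing, the non-responder rates are 0.35 × 0.95 = 33.25% and 0.35 × 0.70 = 24.5%. Fisher's test then rejects in 16.7% of trials. With 15% missing in both arms it rejects in 4.0%.

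**6. Can the choice decide the result?** Suppose 47/85 vs 15/43 respond among observed cases: p = 0.039. With missing subjects as non-responders, 47/100 vs 15/50 gives p = 0.054.

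**7. What each pre-specified analysis assumes.**
- MI: missingness may depend on treatment and observed scores but not on the missing month-12 value. This is missing at random (MAR), not MCAR.
- Observed cases: within arm, completers represent everyone.
- Per-protocol repeat: run only if the PP and ITT sets differ by at least 10% (SAP 2.4.1), and it requires a completed month-12 assessment (SAP 2.2.2).

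None lets a missing subject do worse than the observed data predict.

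**The case against.** Several points on the other side have force.

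- **Disclosure.** A reader might infer that the change was concealed. The documents do not support that. The revision history logs it and SAP 2.1 makes the primary method clear. SAP 2.8 reads as a sentence that was not updated.
- **MI is not observed cases.** A reader might infer that MI simply gives treated dropouts the treated completers' rate. It need not, because the model uses month 7 and 9 scores. As an assumed illustration, let 15% of the treated arm drop out, mostly after poor month-9 scores, with completers at 75% and dropouts imputed at 39%. MI gives 0.85 × 75% + 0.15 × 39% = 69.6%, observed cases 75%, and non-responder imputation 0.85 × 75% = 63.75%. Dropout linked to observed failure is therefore reflected. The gap is dropout linked to outcomes that were never observed, including dropout before month 7.
- **BOCF is not always conservative.** Steps 4 and 5 show it favouring treatment when controls leave more often. This stands, and it shapes the fix.
- **Robustness could still be examined.** SAP 2.1.2 allows further supportive analyses after approval without an amendment, and withdrawal reasons are summarized (SAP 2.3.1). So it would be too strong to say that robustness cannot be shown; the analysis is merely not pre-specified.
- **Dropout may be modest.** Subjects who complete are offered an extension study in which controls can be treated, an incentive to stay. Outcome-related dropout is plausible, not established.

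**Conclusion.** The point holds in this form. SAP 2.8 is incorrect about the primary analysis, the current protocol and SAP disagree on the primary imputation, and the protocol's lack-of-effect assumption is tested by no pre-specified analysis.

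The size is modest under the planning assumptions. With 15% missing in each arm the difference falls by 5.25 points (35 − 29.75), and power falls from 95.4% to 92.4%, still above the planned 90%. A reader might take 97.9%, the power with 100/50 fully observed, as the starting point; that is not like for like, because it assumes no missing data. The effect becomes material only with heavier dropout among treated subjects: 22.75 points and 72% at an assumed 20%/5%, a split that respects the planned 15% overall but has no other support in the documents. With heavier control dropout the direction reverses. These figures assume completers respond at 70% and 35%.

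**What to change.** - Correct SAP 2.8 to state the change from BOCF to MI and the reason for it.
- Reconcile Protocol 10.6 with the SAP, and update the protocol version cited in SAP 1.1.
- In SAP 2.4.3, replace MCAR by MAR given treatment and observed scores. No computation changes.
- Keep MI as the primary method.
- Pre-specify a missing = non-responder analysis on the full ITT set, together with an arm-specific variant such as a tipping-point table that varies the assumed response of missing subjects separately by arm. The second part is needed because non-responder imputation alone is not conservative when control dropout is higher.

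The cost is SAP wording, a protocol amendment or note to align 10.6 (Protocol 12.3 asks for a dated, version-controlled amendment unless the change is administrative), and one or two extra tables from data already collected. Those tables may look less favourable than the primary result.
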